13.1 Disposition of Subjects

The disposition of all subjects in the safety population will be summarised including number of subjects randomised, number completing the study by treatment, and number withdrawn from the study.

All subjects who withdraw or are withdrawn from the study will be listed by treatment, with the reason for withdrawal.

A listing of analysis populations will be provided.

13.2 Protocol Deviations

Before closing the database, data listings will be reviewed to identify any significant deviations and determine whether the data should be excluded from any analysis populations.

Major protocol deviations include subjects who:

- Entered the study even though they did not satisfy the entry criteria.
- Met the criteria for withdrawal from the study but were not withdrawn.
- Received the wrong treatment or incorrect dose.
- Received an excluded concomitant therapy.
- Received investigational product(s) past the expiration date.
- Had their treatment assignment unblinded.

In addition, subjects with minor time deviations (measurements taken outside the allowable windows) will be identified. Allowable time windows for pharmacokinetic samples and other procedures are given in section 8.4 of the study protocol.

13.3 Demographic and Baseline Characteristics

Demographic and baseline characteristics (e.g. physical examination, vital signs and ECGs) will be listed and summarised.

Subjects who take concomitant medication will be listed. All non-trial medication will be coded using version September 2017 of the World Health Organisation (WHO) Drug Global dictionary.

13.4 Treatment Compliance

Dates and times of dosing will be listed.

14 Safety Analyses

Summaries and listings of safety data will use the safety population.

14.1 Extent of Exposure

The dates and times of treatment dosing will be listed to indicate exposure to the study medication.

14.2 Adverse Events

Adverse events will be coded using the version 21.0 or higher of the Medical Dictionary for Regulatory Activities (MedDRA).

All adverse events will be listed.

The number of subjects with at least one treatment-emergent adverse event (TEAE) will be tabulated by actual treatment and MedDRA system organ class. A treatment-emergent adverse event is defined as an event emerging during treatment having been absent pre-treatment or having worsened relative to pre-treatment¹.

For each of the following, the number of adverse events and the number of subjects with adverse events will be summarised:

- TEAEs by system organ class and preferred term
- TEAEs by system organ class, preferred term and severity
- Drug-related (“related” as recorded by the Investigator) TEAEs by system organ class and preferred term

Subjects with more than one TEAE will be counted only once, at the greatest severity or causality, for each system organ class/preferred term. Multiple TEAEs in a subject will be counted once per system organ class and preferred term. Adverse events with missing severity and/or causality will be treated as severe and related, respectively.

Summaries will be sorted by system organ class and decreasing total incidence of preferred term.

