receiving placebo reported dry eye (n=1). All eye disorders AEs were of mild to moderate intensity, resolved spontaneously (without treatment), and were more frequently reported with highest dose (40 mg). Among them, the AEs of blurred vision, photophobia (“Increased ocular light sensitivity”), visual impairment (“distorted contrast perception”, “distorted colour perception”) reported by 8 out of 47 subjects receiving emodepside were considered as treatment-related by the Investigator. Also of note, at the highest dose (40 mg), lightheadedness (n=1), dizziness (n=1) or headache (n=1) were reported concomitantly to blurred vision.

None of the volunteers met any of the protocol-specified withdrawal criteria and overall tolerability to emodepside has been acceptable up to 20 mg. The presence of post-dose visual disturbances in subjects of Cohort 8 receiving either 40 mg solution or placebo may warrant some concern and escalation was stopped at this dose level.

The pharmacokinetic results obtained so far show that T_{max} for the LSF solution is consistently about 1 h post-dose when fasted. Mean C_{max} and AUC for the LSF solution have been roughly dose-proportional, with low to moderate inter-individual variability. The plasma half-life during the first 24 h is very short for a single dose of emodepside. After 3, 7, 16 and 47 h the maximum plasma concentration is reduced to 50%, 25%, 12.5% and 6.25% respectively. Terminal plasma half-life is 523 h. Although data of Cohort 9 (which was treated with a single dose of emodepside with food) are still under review, administration of the LSF of 10 mg with a high fat, high-calorie meal resulted in a clinically relevant food effect with a reduction of AUC to ~67%, C_{max} to 42% and a delay of the T_{max} up to 2.33 h. Therefore, the recommendation of administration of the emodepside (LSF) under fasted conditions is given.

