- Leptin and prolactin will also be measured at Screening Visit 1 and Day 9, as part of the insulin blood sample.
8. Administration of the study medicine will be done in fasting conditions on Days 0-9 at approximately the same time each morning (\pm 15 mins):
- in Cohorts 1 & 2, emodepside will be given in the morning only
 - in Cohort 3, emodepside will be given in the morning and evening (at 12 h intervals). On the last day (day 9), emodepside will be given only in the morning
9. 12-lead ECGs will be recorded in triplicate (with 1 minute between recordings) at -24 h (Day -1) before the morning dose on Days 0 and 9; single recordings will be made at all other time points. ECGs will be recorded:
- at Screening Visit 1 and at Follow-up (Day 30 \pm 2 days)
 - on Day -1: at -24, -23.5, -23, -22.5, -22, -21, -20, -16 and -12 h before the morning dose on Day 0
 - on Day 0: before and at 0.5, 1, 1.5, 2, 3, 4, 8 and 12 h after the morning dose
 - on Days 1-8: before the morning dose
 - on Day 9: before and at the following times after the morning dose: 0.5, 1, 1.5, 2, 3, 4, 8, 12, 24 (Day 10), 72 (Day 12) and 120 h (Day 14) after the Day 9 dose
- Subjects should rest in the supine position for 10 minutes before ECG measurements.
10. Vital signs will comprise blood pressure (BP) and heart rate (HR) at all time points, with oral temperature included at screening and -24 h before the morning dose on Day 0 (Day -1). Subjects should rest in the supine position for 10 minutes before single BP and HR measurements are taken. Vital signs will be measured:
- at the first screening visit and at Follow-up (Day 30 \pm 2 days)
 - on Day -1: at -24, -23.5, -23, -22.5, -22, -21, -20, -16 and -12 h before the morning dose on Day 0
 - on Day 0: before and at 0.5, 1, 1.5, 2, 3, 4, 8 and 12 h after the morning dose
 - on Days 1-8: before the morning dose
 - on Day 9: before and at the following times after the morning dose: 0.5, 1, 1.5, 2, 3, 4, 8, 12, 24, 36 (Day 10), 48 (Day 11), 72 (Day 12), 96 (Day 13) and 120 h (Day 14)
 - at outpatients visits on Days 17, 20, 23 and 27 (\pm 2 days), and long-term follow-up visits (Days 60, 90 and 120 \pm 2 days)
11. Adverse event monitoring will be done throughout the study, but scheduled questioning will be done at the following time points:
- at Screening Visit 1 and at Follow-up (Day 30 \pm 2 days)
 - on Day -1, at -24, -23, -22, -21, -20, -18, -16, -12 h before the morning dose on Day 0

Protocol Version/Date: Version 5, 25 July 2018

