10.6.5. Adverse events

Throughout the study, all AEs observed by either medical staff or professional collaborators, or reported by the subject spontaneously or in response to a direct non-leading question, will be evaluated by the Investigator and noted in the AE section of the CRF, as described in Section 12.2.

AEs will be coded using the version of the Medical Dictionary for Regulatory Activities (MedDRA) current at the time of database lock.

All AEs will be listed.

An AE will be considered as treatment emergent if it appeared after the first dosing, or if appeared before dosing and worsened after dosing. In case of missing onset date of AE or missing onset time of AE when it appeared the first dosing day, the AE will be considered as treatment emergent (TEAE).

The number of subjects with at least one TEAE will be tabulated by actual treatment and MedDRA system organ class and preferred term.

For each of the following, the number of AEs and the number of subjects with AEs will be summarised by actual treatment as follows:

- TEAEs, by system organ class and preferred term
- drug-related TEAEs, by system organ class and preferred term

Subjects with more than one TEAE will be counted only once, at the maximum causality, for each system organ class and preferred term. AEs with missing severity and/or causality will be treated as severe and possibly related, respectively.

AEs leading to withdrawal, deaths and SAEs will be listed separately (fatal events will be listed separately from non-fatal events).

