12.1 Premature Withdrawal and Missing Data

All subjects who withdraw prematurely from the study or study drug will be included in the statistical analyses.

If a subject completes the treatment period but has missing data, then this will be made apparent in the subject listings. Missing data will not be imputed except for as outlined in Section 12.2.

If the study is prematurely discontinued, all available data will be listed and a review will be carried out to assess which statistical analyses are still considered appropriate.

Data collected at unscheduled time points during the study will not be used in the summaries or data analyses. They will be included in the listings.

If time information (i.e. hours and/or minutes) for adverse events or concomitant medication is missing, but the day is present, then the time will be calculated in days. If date information is partial or missing, then any derived times (e.g. AE start time from last study medication) will be listed as missing.

Conventions for handling missing plasma concentrations are given in Appendix B.

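### SAP 14.2 defines treatment-emergent AEs differently from Protocol 10.6.5 without saying so; read literally, AEs starting after the last dose would be missing from every AE summary table

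*SAP*

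**What the plan says.** **Protocol 10.6.5.** "An AE will be considered as treatment emergent if it appeared after the first dosing, or if appeared before dosing and worsened after dosing". No end date follows. The next sentence, which begins "In case of missing onset date of AE", makes such an event treatment-emergent by default. It does the same when only the onset time is missing on the first dosing day.

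**SAP 14.2.** A treatment-emergent AE is "an event emerging during treatment having been absent pre-treatment", or one that is worse than it was before treatment. The section does not say when treatment ends and gives no default for a missing onset. The nearest rule is in SAP 12.1: "If date information is partial or missing, then any derived times" are shown as missing. That rule does not classify the event.

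**Where the definition is used.** AEs are the only entry under primary safety endpoints in Protocol 2.2.1, and they head the longer primary list in SAP 4.2.1. SAP 18.1 plans three AE summary tables: 14.3.1.1 (all), 14.3.1.2 (drug-related) and 14.3.1.3 (by severity). All three are limited to treatment-emergent AEs.

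**Timing.** Dosing covers Days 0 to 9. For Cohort 3, Table 2 of the protocol says "On the last day (day 9), emodepside will be given only in the morning". Protocol 4.3 and 7.1 still list an evening dose through Day 9 and need reconciling with that, but the last dosing day is Day 9 on either text. Protocol 8.6.4 ends the AE reporting period at the Day 120 visit. It also asks for later AEs to be reported if the investigator judges them possibly related.

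**Duty to flag.** SAP section 3 undertakes to identify substantial differences in method from the protocol. The introduction to Protocol section 10 lets the SAP modify the plan, but requires an amendment for a major change to the primary endpoint or its analysis.

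**The concern.** Two programmers, one working from Protocol 10.6.5 and the other from SAP 14.2, could set the treatment-emergent flag differently for the same event. The flag decides which events enter the summary tables of the primary endpoint.

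The difference affects a part of the study that was planned for safety reasons. Protocol 1.5 explains the follow-up to Day 120 by a terminal half-life of more than 520 h. The on-study ophthalmology examination is on Day 10 (Protocol 8.5.4) and the full neurological examination before discharge is on Day 14 (8.3.9). Clinically significant findings at either are reported as AEs. Eye and nervous system disorders were the most frequently reported treatment-emergent AEs in the first eight cohorts of the single-dose study (Protocol 1.4). A new eye AE with onset recorded at the Day 10 visit is therefore a realistic example of an event that one definition tabulates and the other may not.

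**Working it through.** The plan gives no figure to reproduce here, and there is no formal sample size calculation. The check compares the two rules and then counts what lies between them.

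**1. The two rules side by side**

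| Event | Protocol 10.6.5 | SAP 14.2, read literally |
|---|---|---|
| New onset, Days 0–9 after first dose | Emergent | Emergent |
| Onset on Days 0–9, continuing later | Emergent | Emergent |
| New onset after the last dose | Emergent | Not emergent |
| Present before dosing, worse after the last dose | Emergent | Unclear: the worsening clause can be read without the during-treatment limit |
| Onset date missing | Emergent by default | No rule |

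**2. Scheduled AE questionings after the first dose** (Protocol Table 2, footnote 11)

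- Day 0, at 1, 2, 3, 4, 6, 8 and 12 h: 7
- Days 1–8, before the morning dose: 8
- Day 9, pre-dose and at 0.5, 1, 2, 3, 4, 6, 8 and 12 h: 9
- Through Day 9: 7 + 8 + 9 = 24
- Days 10–14, at 24, 36, 48, 72, 96 and 120 h after the Day 9 dose: 6
- Days 17, 20, 23, 27, 30, 60, 90 and 120: 8
- After Day 9: 6 + 8 = 14
- Share outside a Day 0–9 window: 14 / (24 + 14) = 14/38 = 36.8%

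The count depends on the boundary chosen. If treatment were taken to run one 24 h interval past the last dose, including the 24 h time point, 13/38 = 34.2% would lie outside. Protocol 8.2 adds questioning whenever blood is drawn, so 38 is the footnote schedule and not every contact.

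**3. Calendar time**

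Days 10–120 are 111 of the 121 days from Day 0 to Day 120: 111/121 = 91.7%. This measures time, not events.

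**4. Why the number of AEs lost cannot be computed**

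Let r be the daily rate of new AEs after Day 9 relative to Days 0–9. The share of onsets lost is 111r / (10 + 111r). The documents give no value for r. Taking r as an assumption, the share is 0% at r = 0, 11.1/21.1 = 53% at r = 0.1 and 111/121 = 92% at r = 1. The range is too wide to serve as an estimate.

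**5. Drug persistence**

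Protocol 1.4: "Terminal plasma half-life is 523 h". From Day 9 to Day 30 is 21 × 24 = 504 h, and 2^(−504/523) = 0.51. From Day 9 to Day 120 is 111 × 24 = 2,664 h, or 5.1 half-lives, and 2^(−2664/523) = 0.03. Both fractions refer to the terminal-phase component only.

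**The case against.** **The SAP states no Day 9 cut-off.** A reader might infer that it does. Section 14.2 contrasts treatment with pre-treatment, names no post-treatment category, and cites a general guideline for the wording. The dummy row in the SAP's AE listing template also marks an event 10 d 7 h after the last dose as treatment-emergent, against the strict reading. That evidence is weak: the row prints a duration of 34 d 4 h 5 min where its own dates give 32 d 18 h 45 min, and it uses a causality category the study does not have. The objection stands to this extent: the text is ambiguous, and an intended exclusion is not shown.

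**Not every AE on Days 10–120 would drop out.** Only events with onset after treatment are at risk. Those that began on Days 0–9 and continue stay in.

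**The loss is from tables, not from the record.** All AEs are listed. Deaths, SAEs, other significant AEs and AEs leading to withdrawal are also listed without a treatment-emergent restriction (SAP 14.2 to 14.4). With up to 24 subjects and no formal testing of safety data, late events would remain visible. This stands, but listings give no counts by treatment group.

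**The large figures can mislead.** The 92% is calendar time. Treatment-related AEs in the first eight single-dose cohorts resolved within 24 h, and Cohort 10 eye AEs mostly began near Tmax. Nor does half of peak exposure persist at Day 30: Protocol 1.4 puts concentration at 6.25% of maximum by 47 h after a single dose, and Protocol 1.5 gives a dominant half-life of about 11 h. All of this stands, although single-dose experience need not carry over to ten days of dosing.

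**The missing-onset rule will rarely be used.** Subjects are resident from Day −3 to Day 14, so missing dates should be few in that period. This is fair, but outpatient follow-up lasts far longer, and the protocol's default costs nothing to keep.

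**Conclusion.** The conflict is real and unflagged. The protocol's rule has a start and no end, and covers missing onset. The SAP's rule ties emergence to treatment, leaves the end of treatment undefined, and has no missing-onset rule. Read literally, AEs with new onset after the last dose on Day 9 would be absent from Tables 14.3.1.1 to 14.3.1.3, the only AE summary tables for the primary endpoint, while remaining in the listings.

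On that reading 14 of 38 scheduled questionings after the first dose (37%) fall outside the window, including both on Day 10. This assumes that treatment means the dosing days, 0 to 9, and that the schedule in footnote 11 is the right base. The number of AEs affected is unknown. No inferential result changes, because safety data are only described.

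This is more than missing detail, because the choice of rule changes which events reach the primary-endpoint tables. It should be settled before the first unblinding, since Cohorts 1 and 2 are locked and analysed apart from Cohort 3 and both analyses need the same flag. No explanation of the change appears in the SAP text available for this review; parts of the document were not included, so one there cannot be ruled out.

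**What to change.** In SAP 14.2, replace the definition with the protocol's: onset after the first dose, or onset before it with worsening afterwards, with no upper time limit. An upper limit at the Day 120 visit should not be added. Protocol 10.6.5 has none, and it would exclude the later, possibly related AEs that Protocol 8.6.4 asks to be reported.

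Restore the protocol's default that a missing onset date, or a missing onset time on the first dosing day, makes the AE treatment-emergent.

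Optionally, show counts with onset on Days 0–9 and from Day 10 onward in separate columns, so that the on-treatment picture is kept without losing late events.

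If a narrower window is intended, the SAP should define its end, flag the departure as section 3 promises, and address whether Protocol section 10 then requires an amendment.

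The cost is one or two sentences in the SAP and one derivation rule for the treatment-emergent flag. No data collection changes.

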14.3 Deaths, Serious Adverse Events and Other Significant Adverse Events

Deaths and serious adverse events will be listed separately (fatal events separate from non-fatal events). Other significant adverse events, as identified by the investigator in the CRF, will be listed separately.

14.4 Adverse Events Leading to Withdrawal from the Study

Adverse events leading to withdrawal will be listed separately.

14.5 Clinical Laboratory Evaluations

Data from haematology, clinical chemistry, coagulation and urinalysis will be summarised by treatment.

Urinalysis parameters will also be listed.

All laboratory values of potential clinical importance will be listed and all related laboratory results (i.e. haematology, coagulation or clinical chemistry) for subjects with values of potential clinical importance will be listed, separately. Frequencies of laboratory values of potential clinical importance will be summarised.

14.6 Other Safety Measures

14.6.1 Vital signs

Vital signs at each planned assessment, and change in vital signs from baseline at each planned post-baseline assessment, will be summarised by treatment.

Vital signs data of potential clinical importance will be listed.

14.6.2 ECG

QT interval data will be presented using Bazett's (QTcB) and Fridericia's (QTcF) corrections.

ECG data will be summarised by treatment and time point. Differences from baseline (Day 0 pre dose) will be summarised by treatment and time point.

The number of subjects with a potentially clinically important ECG value will be summarised by actual treatment and time point, giving the numbers of subjects with QT, QTcB or QTcF > 450 msec, > 480 msec and > 500 msec, and the numbers of subjects with increases in QT, QTcB or QTcF from baseline of > 30 msec and > 60 msec³. A supporting listing of all subjects with an ECG value of potential clinical importance and a separate listing of ECG findings classified as abnormal by the Investigator will also be provided.

14.6.3 Physical examination

Abnormal physical examination findings will be listed.

14.6.4 Neurological examination

Abnormal neurological examination findings will be listed.

14.6.5 Ophthalmology examination

Abnormal ophthalmology examination findings will be listed.

15 Pharmacokinetic Analyses

Analytical Services International Ltd will measure the plasma concentrations of emodepside. The pharmacokinetic analysis will be done by Statistics and Data Management Department at HMR. Pharmacokinetic parameters will be calculated using WinNonlin, version 7.0 or higher.

The pharmacokinetic parameters to be derived are given in Appendix B.

PK concentration data will be summarised using the PK concentration population. PK parameters will be summarised using the PK parameter population.

For log normally distributed parameters, the primary measure of central tendency will be the geometric mean⁴; for other parameters, it will be the arithmetic mean or median.

For all variables N (number of subjects receiving the treatment/formulation in the population), n (number of observations), arithmetic mean, median, minimum, maximum, SD, %CV, and the 95% confidence interval for the arithmetic mean will be provided. For log-transformed variables, all of the above plus the geometric mean, which is the anti-logged arithmetic mean of log-transformed variables, its 95% confidence interval and the SD of the logs will be provided.

The between-subject CV will be calculated using:

1. $\%CV_b = 100 * (SD/Mean)$ with SD and Mean of untransformed data

2. $\%CV_b = 100 * \sqrt{\exp(SD)^2 - 1}$ with SD of log-transformed data

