 16. Use of dietary supplements or herbal remedies (such as St John's Wort) that are known to be inducers or inhibitors of CYP3A4, or other co-medications known to be relevant substrates of CYP3A4, during the 28 days before the first dose of study medication (see list in the Study Procedures Manual)
 17. Use of dietary supplements or herbal remedies (such as St John's Wort) that are known to be strong inhibitors of P-gp, or other co-medications known to be relevant substrates of P-gp, during the 28 days before the first dose of study medication (see list in the Study Procedures Manual)
 18. Relevant pathological abnormalities in the ECG at screening, such as:
 - second or third-degree atrioventricular (AV) block; or
 - prolongation of the QRS complex > 120 msec; or
 - QTc-interval (QTcB or QTcF) > 450 msec.
 19. Evidence of drug abuse (via urine testing) at the screening assessment or admission to the ward
 20. Use of excluded therapies that may impact on the interpretation of study results in the opinion of the Investigator or Sponsor
 21. Objection by General Practitioner (GP) to subject entering trial
 22. History of residing for 6 or more continuous months during the last 3 years in regions with endemic parasitic infections, as determined by the Investigator
 23. Possibility that subject will not cooperate with the requirements of the protocol
 24. Wearing of contact lenses during the 1 month before the first dose of study medication. Contact lens wear is not permitted during the study
 25. Presence of an ocular disorder for which topical ocular therapy is currently or

chronically prescribed, including inflammatory eye disease (dry eye allergic conjunctivitis [seasonal allergic conjunctivitis, vernal keratoconjunctivitis, atopic keratoconjunctivitis], uveitis and glaucoma)

26. History of ocular disease requiring ongoing treatment
27. Past ocular surgery, including laser or other refractive corneal surgery
28. Evidence of eye irritation, visual difficulties, corneal opacity, ocular surface (corneal or conjunctival damage, with or without ocular symptoms)
29. Evidence of narrow anterior chamber angles causing increased risk of acute glaucoma
30. Evidence of ocular media opacity including lens opacity/vitreous opacities
31. Evidence of retinal or optic nerve pathology
32. Evidence of pronounced colour blindness, as indicated by an Ishihara score of 9/13 or below

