10.5. Demographics and Other Baseline Characteristics

Demographic and baseline characteristics (eg medical history, physical examination, vital signs, weight, ECGs and ophthalmology results) will be summarised.

Subjects who take concomitant medication will be listed. All non-trial medication will be coded using the World Health Organisation Drug Dictionary (WHO DD).

Medical history will be coded using the version of the Medical Dictionary for Regulatory Activities (MedDRA current at the time of database lock).

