10.6. Safety Analysis

Safety and tolerability data will be summarized using the following parameters:

- Vital signs;
- 12-lead ECG;
- Haematology;
- Clinical chemistry;
- Coagulation;

- Urinalysis;
- Physical examination;
- Neurological examination;
- Ophthalmology assessments;
- AEs.

No formal hypothesis testing of these parameters will be carried out.

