4.2 Study Endpoint(s)

4.2.1 Primary Endpoint(s)

- Adverse events (AEs)
- Physical examination findings
- Neurological examination findings (including assessments of tremor of the hands and fingers, coordination/cerebellar function (finger to finger, finger to nose, with eyes open and closed), pupil size and reaction to light)
- Vital signs: heart rate (HR), systolic and diastolic blood pressure (BP)
- 12-lead ECG (including heart rate (HR), PR, QRS, QTcB, QTcF)
- Clinical laboratory tests:
 - Haematology: haemoglobin, haematocrit, mean corpuscular volume (MCV), mean corpuscular haemoglobin (MCH), mean corpuscular haemoglobin concentration (MCHC), platelets, reticulocytes, white blood cells (WBC) including differential, red blood cells (RBC), glycated haemoglobin (HbA1C; at screening only);
 - Coagulation: activated partial thromboplastin time (aPTT), prothrombin time (PT);
 - Biochemistry: serum aspartate aminotransferase (AST), alanine aminotransferase (ALT), alkaline phosphatase (AP), glutamate dehydrogenase (GLDH), gamma-glutamyl transpeptidase (GGT), lactate dehydrogenase (LDH), creatine kinase (CK), amylase, lipase, free T3 and T4, thyroid-stimulating hormone (TSH), glucose, cholesterol (HDL, LDL, total), triglycerides, creatinine, urea, uric acid, bilirubin (total and conjugated), total protein, sodium, potassium, calcium, chloride, and magnesium;
 - At baseline (screening visit 1) and Day 9 additional hormones: leptin and prolactin levels
 - Urinalysis: by dipstick – glucose, ketone bodies, specific gravity, occult blood, pH, proteins, leucocytes, bilirubin, urobilinogen, nitrites.
- Ophthalmology assessments: including visual symptoms, past ocular history, best corrected distance visual acuity, colour vision assessment, Amsler grid assessment

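### The protocol says ophthalmology will be summarised, but the SAP plans only a listing of abnormal findings, so a change from screening to Day 10 judged normal reaches no by-treatment summary

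*SAP*

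**What the plan says.** **Protocol.** Section 10.6 opens its list with "Safety and tolerability data will be summarized using the following parameters", and "Ophthalmology assessments" is an item on that list. The Statistics entry of the Protocol Summary has the same item. Section 10.5 says of baseline data: "eg medical history, physical examination, vital signs, weight, ECGs and ophthalmology results) will be summarised". No later subsection of 10.6 says how ophthalmology is to be presented. Section 8.5.4 places the examination at Screening Visit 2 and Day 10, and section 4.3 says the assessments are repeated on Day 10 without mydriatic drops. The Ishihara test is placed at Screening Visit 1 (section 8.3.1 and note 5 to the schedule of events).

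**SAP.** Section 4.2.1 names "best corrected distance visual acuity, colour vision assessment, Amsler grid" among the primary endpoints; protocol 2.2.2 classes the same assessments as other safety endpoints. Section 14.6.5 consists of the sentence "Abnormal ophthalmology examination findings will be listed". Section 18.1 provides Listing 16.2.9.6 for it, and the shell (L_PE1_PG) restricts that listing to abnormal results. Section 13.3 describes the baseline summary with "e.g. physical examination, vital signs and ECGs) will be listed and summarised", without ophthalmology. Section 10 names active versus placebo as the comparison of interest. Section 3 says that substantial differences from the protocol's methods will be identified.

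**The concern.** Acuity and colour vision can move without leaving the range an examiner calls normal. A listing restricted to abnormal rows has no denominators, no change from screening and no comparison of groups. The single-dose study gave reason to look at these functions: protocol 1.4 reports blurred vision and altered contrast and colour perception judged treatment-related, and reduced visual acuity in Cohort 10. Protocol 1.5 links the stop in single-dose escalation to visual and nervous system disturbances.

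At stake is whether the report of a 10-day repeat-dose trial shows, arm by arm, what happened to measured visual function. As planned, a reader would have to assemble that from the complete listings.

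**Working it through.** There is no planned sample size, power or error rate to reproduce here. The check compares the planned outputs with the commitments.

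**Step 1. Planned outputs (SAP 18.1 and the shells)**

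| Safety data | Summary table with change from baseline | Listing |
|---|---|---|
| Chemistry, haematology, coagulation | Yes (T_LB2) | Yes |
| Vital signs | Yes (T_VS1) | Yes |
| ECG | Yes (T_EG2, T_EG3) | Yes |
| Ophthalmology | None, and no figure | 16.2.9.6, abnormal results only |

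SAP 12.4 defines potential clinical importance for laboratory values, vital signs and QT intervals. It gives no rule for ophthalmology, so entry to Listing 16.2.9.6 rests on the examiner's classification.

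**Step 2. Where a change between screening and Day 10 would appear**

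- Symptom reported by the subject: adverse event tables 14.3.1.1 to 14.3.1.3, as applicable, by treatment.
- Examination abnormality judged clinically significant: reported as an adverse event (protocol 8.5.4), so in those tables, and in Listing 16.2.9.6.
- Abnormality not judged clinically significant: Listing 16.2.9.6, not tabulated.
- Change with the Day 10 result judged normal: only in the complete listings of all data promised at the end of SAP 18.1.

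The last two routes have no by-treatment summary. The last is also absent from the dedicated listing.

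**Step 3. Size of the single-dose signal (protocol Table 1, Cohorts 1 to 8)**

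- Eye disorders on emodepside: 1 (5 mg tablet) + 2 (10 mg LSF) + 1 (20 mg LSF) + 5 (40 mg LSF) = 9 of 47, or 19.1%. Placebo: 1 of 16, or 6.3%. Total 10 of 63, matching the table.
- At 40 mg: 5 of 6. At all lower doses: (9 − 5)/(47 − 6) = 4/41, or 9.8%.
- Nervous system disorders: 10 of 47 (21.3%) on emodepside and 2 of 16 (12.5%) on placebo; 3 of 6 at 40 mg.
- Judged treatment-related on emodepside (protocol 1.4): eye 8/47 (17.0%), nervous system 7/47 (14.9%).

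The two classes are of similar overall frequency, so eye disorders are one of two leading signals.

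**Step 4. What a summary table could show**

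If changes are roughly normal with standard deviation s, the 95% half-width for a mean change is t(0.975, n − 1) × s/√n:

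- n = 6 (one active arm): 2.571/2.449 = 1.05 s.
- n = 4 (placebo OD in table A, if the 2 + 2 subjects share the SAP's OD label): 3.182/2 = 1.59 s.
- n = 2 (placebo BID in table B): 12.706/1.414 = 8.98 s.

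The table can therefore display individual shifts and a common direction within an arm. It cannot support a formal comparison, and none is planned for safety data.

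**The case against.** **The protocol uses the verb loosely.** Physical and neurological examinations are on the same list in 10.6, yet 10.6.4 specifies only a listing of abnormal findings for them, and SAP 14.6.3 to 14.6.5 treat all three examinations alike. This has weight. But 10.6.4 does not cover ophthalmology, and 10.5 names ophthalmology results separately, so the general commitment stands.

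**The SAP may change protocol plans.** The opening of protocol section 10 allows it. A reader might infer that a protocol amendment was required because the SAP calls these primary endpoints. The documents do not support that: protocol 2.2.1 has adverse events as the only primary endpoint. The fault is that a reduction is neither identified nor explained. Some SAP pages were not available for this review, so this can be said only of the text that was. The baseline lists in protocol 10.5 and SAP 13.3 are also examples, so the omission in 13.3 is not an exclusion.

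**The data are kept.** A reader might infer that normal values are lost, or that the question can no longer be answered. Neither follows, because complete listings are planned. The loss is of a summary.

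**The single-dose signal is already covered.** Those counts are adverse events, which the SAP tabulates by treatment. Most came at 40 mg, while this trial is limited to 20 mg per day. Treatment-related events in Part 1 resolved within 24 h, so an examination about a day after the last dose would mainly show persisting effects. All of this stands. It limits the point to measured change that is not reported as an event.

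**Colour vision.** A reader might infer that a subject could lose several Ishihara plates unnoticed while staying above the entry limit, "as indicated by an Ishihara score of 9/13 or below". The documents do not support this. The Ishihara test is documented only at Screening Visit 1, and the limit is an exclusion criterion, not a definition of an abnormal Day 10 result. The content of the Day 10 colour assessment is left to the Study Procedures Manual.

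**Conclusion.** The mismatch is real and specific. Three places in the protocol commit to a summary, the SAP lists the measures under primary endpoints, and the planned ophthalmology output is zero tables, zero figures and one listing limited to abnormal results. The consequence is moderate: no values are lost and symptomatic effects are tabulated, but a change in measured visual function judged normal on Day 10 would not be summarised against placebo.

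This rests on two assumptions: that acuity is recorded as a score at both screening and Day 10, and that the unavailable SAP pages do not flag the change. A paired colour-vision score is not assumed.

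**What to change.** Add one table shell to SAP 14.6.5 and 18.1, produced as A for Cohorts 1 and 2 and B for Cohort 3. A single table of all three dose levels beside one pooled placebo group would conflict with the separate locks and reports in SAP 7.2 and 18.1.

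- Rows: best corrected distance acuity, colour vision, Amsler grid and visual symptoms, at screening and Day 10.
- Change for scored tests and shift from screening for categorical ones, by treatment including placebo, with the number assessed.
- Baseline for each test: the screening visit at which that test was done. Give colour-vision change only if the same test is repeated on Day 10.
- State that the table is descriptive.

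Name ophthalmology in the SAP 13.3 baseline summary and keep Listing 16.2.9.6. If the sponsor prefers a listing alone, the SAP should identify and justify the departure, as its section 3 promises.

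The cost is one shell and its programming. No assessment, visit or data item is added.
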